### Table 26: Summary of Clinical Worsening Analysis

Variable	Model	Population	Factors
Time to clinical Worsening	Log Rank	ITT	Treatment Group and stratification by Prostanoid usage.
Time to clinical Worsening	Log Rank	mITT	Treatment Group and stratification by Prostanoid usage.
Time to Death (All-cause mortality)	Log Rank	ITT	Treatment Group and stratification by Prostanoid usage.
Time to Atrial septostomy	Log Rank	ITT	Treatment Group and stratification by Prostanoid usage.
Time to Hospitalization due to worsening of PAH (Adjudicated)	Log Rank	ITT	Treatment Group and stratification by Prostanoid usage.
Time to PAH specific therapy	Log Rank	ITT	Treatment Group and stratification by Prostanoid usage.
Time to decrease in Decrease of >15% from baseline or >30% compared with the last study related measurement in 6MWD	Log Rank	ITT	Treatment Group and stratification by Prostanoid usage.
Time to Worsening of WHO Functional Class (e.g., from Class II to Class III or IV, OR Class III to Class IV)	Log Rank	ITT	Treatment Group and stratification by Prostanoid usage.

### 7.4.2 Change in WHO functional Class

The change from baseline for WHO Functional Class at Week 18 will be analysed by using ANCOVA with treatment group and stratification factor prostanoid usage as factor and baseline WHO functional score as covariates.

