16.3.2. Secondary Efficacy Endpoints

The secondary efficacy endpoints include:

1. TTCW*: The time (in days) from start of treatment to first event (first day the event is noted), with iNO as compared to placebo, measured from baseline to week 18. TTCW event is defined as any of the following:
 - a. Death (all-cause mortality)
 - b. Atrial septostomy
 - c. Hospitalization due to worsening of PAH (adjudicated)
 - d. Start of new specific PAH treatment (endothelin receptor antagonists [ERAs], phosphodiesterase type-5 [PDE-5] inhibitors or prostanoids), an increase in the dose of an ERA or PDE-5, increase in the dose or frequency of an inhaled prostanoids, or an increase in the dose of an intravenous or subcutaneous prostanoids by >10%.
 - e. Decrease of >15% from baseline or > 30% compared with the last study related measurement in 6MWD and should be confirmed by a repeat measurement performed at least 14 days later
 - f. Worsening of WHO Functional Class (e.g., from Class II to Class III or IV, OR Class III to Class IV); and should be confirmed by a repeat assessment at least 14 days later
2. Change in WHO Functional Class, with iNO as compared to placebo, from baseline to 18 weeks.

The TTCW endpoint will be analyzed with log-rank test stratified by the prostanoid usage status. The censoring time points for the analyses include the time points at which subjects drop out of the study or complete the study without any of the specified events.

The WHO Functional Class endpoint will be analyzed with the same method as that for the primary endpoint. Change from baseline to week 18 will also be evaluated as an exploratory analysis.

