**Table 6: WHO Functional Class**

Variables	Module	Source of Data	Baseline Definition	Variable specific derivation	Change from Baseline analysis	Comment (to be removed later)
WHO Functional Class Status	WHO Functional Class assessment	CRF	Week 2 (V2) Assessment	No, CRF data.	Yes	This is not Continuous data

For the second part of the study, change in WHO functional class data from Baseline (week 2) and from week 18 will be analysed at month 4, 8 and 12.

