#### Missing data imputation for secondary endpoint:

For all the other efficacy endpoints, the last observation carry forward (LOCF) approach will be used in handling the missing data as that used in the EARLY study ([Galiè 2008](#)).

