**Table 24: Sensitivity Analysis**

No.	Sensitivity Analysis
1	Primary analysis on Per Protocol Population
2	Primary Analysis on Modified Intention To Treat Population
3	Analysis will be performed with Last Observation Carry Forward (LOCF) approach will be applied for subjects not withdrawing trial due to adverse events, for subjects withdrawing trial due to adverse events (including deaths), worst value (zero for 6MWD) will be assigned at EOS visit.  The analysis will be performed on ITT population.
4	Analysis will be performed with worst-case imputation approach I (i.e. impute the missing value for a subject with worst value (within the subject) for all subjects who withdraw prematurely for any reason. The value of zero for 6MWD will be imputed for all deaths.

No.	Sensitivity Analysis
	The analysis will be performed on ITT population.
5	
Analysis will be performed with worst-case imputation approach II (i.e., impute the missing value for a subject in the active and Placebo dose group by the worst result of all subjects with non-missing assessments in their respective assigned dose groups). The value of zero for 6MWD will be imputed for all deaths.
 
The analysis will be performed on ITT population.

6	
Analysis will be performed with worst-case imputation approach III (i.e. impute the missing value for a subject in the active dose group by the worst result of all subjects with non-missing assessments in the same active dose groups and impute the missing value for a subject in placebo group by his/her last available assessment prior to the missing assessment. The value of zero for 6MWD will be imputed for all deaths.
 
The analysis will be performed on ITT population.

7	Change from Baseline in 6MWD analyzed using the same model as primary for all subjects completing the 18 weeks treatment in ITT and mITT population.
8	Change from baseline (defined as week 1 assessment) in 6MWD analyzed using the same model as primary on ITT population
9	Change from baseline analyzed using the same model as primary for all subjects on IV/SC prostacyclin +/- orals in ITT population.
10	The Change from baseline analyzed using the same model as primary on ITT population for all subjects on one oral treatment (no IV, Inhaled and SC) of either prostacyclin or Endothelin Receptor Antagonists (ERAs) or Phosphodiesterase Inhibitors (PDE 5 Inhibitors)

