## 7.4 Secondary Analysis

All secondary analysis will be performed on ITT analysis set. All missing data will be imputed using Last Observation Carried Forward Rule (LOCF).

For all secondary continuous endpoints if normality assumptions fail then log transformed analysis will be performed. If the normality assumptions still fail, then analysis will be performed on the ranked data.

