#### **Hypothesis:**

$H_0: \mu_{iNO\ 75} = \mu_{Placebo}$  versus  $H_1: \mu_{iNO\ 75} < \mu_{Placebo}$  for at least one realization.

**SAS code:** Same as primary

**Direction of difference:** Smaller the Better.

**Missing Data:** Please refer to Section 6.3 for missing data imputation. Missing values will be imputed using the LOCF.

No.	Sensitivity Analysis
1	Analysis on Modified Intention to treat Population
2	Analysis on mITT population for all the subjects completing the 18 weeks treatment period

Analysis: Similar to primary for WHO functional class (Table 27).

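### Change in WHO Functional Class, third in the testing hierarchy, uses ANCOVA with LOCF and has no rule for death, so death never counts as worsening on this endpoint

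*SAP*

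**What the plan says.** Protocol 16.3.4 and SAP 7.5 test 6MWD, then TTCW, then WHO Functional Class, and stop at the first non-significant result.

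For WHO class, SAP 7.4.2 says "The change from baseline for WHO Functional Class at Week 18 will be analysed by using ANCOVA", with treatment, prostanoid stratum and baseline class in the model. Lower is better. On missing data the same section says "Missing values will be imputed using the LOCF". SAP 7.4 repeats this for all secondary analyses. SAP 6.3 and protocol 16.3.5 share the general rule: "For all the other efficacy endpoints, the last observation carry forward (LOCF) approach will be used in handling the missing data".

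The only value assigned to death anywhere is for walk distance, in sensitivity analyses (SAP 6.3 and Table 24): "The value of zero for 6MWD will be imputed for all deaths". WHO class has two sensitivity analyses, one on the mITT set and one on mITT subjects who complete 18 weeks, plus a descriptive shift table.

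Three further statements bear on the method:

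- Protocol 16.3.2: "The WHO Functional Class endpoint will be analyzed with the same method as that for the primary endpoint". That method is a repeated measures mixed model. SAP 7.4.2 names ANCOVA but refers to the primary analysis for its SAS code, which is mixed-model code.
- SAP Table 6 comments on this variable: "This is not Continuous data".
- SAP 7.4, for continuous secondary endpoints: "if normality assumptions fail then log transformed analysis will be performed". Ranked data follow if normality still fails.

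**The concern.** LOCF fixes a subject who dies at the last class recorded while alive. If that class equals baseline, the change is 0. If it was better than baseline, the subject counts as improved. If decline had already been recorded, at a scheduled or early-discontinuation visit, that decline is kept. In none of these cases does the death itself count.

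The sensitivity analyses leave the gap open. The mITT analysis applies the same rule to a subset, and the completer analysis removes subjects who die before Week 18. The plan does give death a worst value for 6MWD, but nothing comparable for WHO class, which also carries confirmatory alpha.

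At stake is what a WHO class claim would mean. If deaths differ between arms, the Week 18 comparison leaves out the worst outcome, in favour of whichever arm has more deaths.

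**Working it through.** **Planned numbers.** SAP 5.4 plans 150 evaluable subjects and assumes 20% dropout: 150 / (1 − 0.20) = 187.5, rounded up to 188, or 94 per arm. This reproduces the stated figure. Up to about 188 − 150 = 38 subjects could lack Week 18 data and be filled by LOCF. The documents do not say how many would be deaths, and give no effect size, SD or power for WHO class.

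**Effect of the rule on one subject.** Under LOCF a death contributes (last observed class − baseline class), which is 0 when the two are equal.

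**Effect on the arm difference.** Assume 94 per arm, no treatment effect in survivors, SD of change 0.5 class, and last class equal to baseline. Take 6 deaths on iNO and 2 on placebo.

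- LOCF: (6 × 0 − 2 × 0) / 94 = 0.000.
- Death scored +1 class: (6 − 2) / 94 = +0.043, z = 0.55.
- Death scored +2 (for example Class III at baseline, death one step below IV): (12 − 4) / 94 = +0.085, z = 0.92.
- Deaths reversed (2 and 6): −0.043 and −0.085.
- Equal deaths (3 and 3): 0 under every score.

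**Effect on the test.** Simulation on assumed inputs: 94 per arm; baseline class II/III/IV in 25/65/10%; survivor change of −1/0/+1 in 22/70/8% on iNO and 15/73/12% on placebo; last class of those who die equal to baseline; one-sided 0.025 as in protocol 16.3.4. The LOCF column uses a z-test on mean change as a stand-in for the ANCOVA. The other column is an unstratified rank test with every death ranked below every survivor. Results do not condition on 6MWD or TTCW being significant.

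| Deaths, iNO vs placebo | Benefit declared, LOCF | Benefit declared, death ranked worst |
|---|---|---|
| 6% vs 2% | about 27% | about 10% |
| 3% vs 2% | about 28% | about 19% to 21% |
| 2% vs 6% | about 30% | about 46% |

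With no survivor effect, LOCF rejects in about 2–3% of trials whatever the split of deaths.

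At 6% vs 2%, scoring death numerically as 5 and comparing means gives about 4%, not 10%. The answer depends on the number chosen for death, which favours ranks.

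**The log step.** SAP 7.4 limits it to continuous secondary endpoints. There are only two secondary endpoints, and TTCW is tested by log-rank, so if the step applies to anything it applies to WHO class. A change of 0 or −1 has no logarithm.

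**The case against.** The strongest reply is the testing order. WHO class is reached only if 6MWD and TTCW are both significant, and TTCW counts all-cause death and confirmed worsening of WHO class as events. Time to death is also analysed separately (SAP Table 26), and deaths are compared by Fisher's exact test (SAP 7.7.1). This stands as a real limit on exposure. It is not complete protection: TTCW is a six-component first-event composite and can favour iNO through non-fatal events despite more deaths. The separate death analyses do not change what the WHO class test measures.

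Second, even the primary 6MWD analysis gives death no value; zero appears only in sensitivity analyses. True, but WHO class lacks even that.

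Third, the Table 6 remark sits in a comment column marked for later removal, and treating four ordered classes as scores is common practice. In the simulation, LOCF with a rank test gives about 26% against 27% with the z-test, so replacing ANCOVA alone changes almost nothing. The missing death rule is what matters.

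Fourth, the log step may not be meant for WHO class, and ranked data are already the last fallback. This is a fair reading, so the text needs clarifying; it does not show that a log analysis would be run.

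A reader might also infer that LOCF scores every death as stable, or that it inflates false positives for iNO. The documents support neither. WHO class is recorded at every visit and at early discontinuation, so the carried value can be a worsening. With no survivor effect the rejection rate stays near nominal.

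**Conclusion.** The gap is real and should be closed before unblinding. As written, a confirmatory endpoint records death as the last living class, and no planned WHO analysis corrects it.

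The direction of the bias is not known. On the assumed inputs, LOCF favours iNO if iNO has more deaths (27% against 10%) and works against iNO if placebo has more (30% against 46%). With nearly equal deaths the gap is smaller. These figures rest on assumed death rates, baseline mix and survivor effect. Much of the 27% is power for the survivor benefit built into the simulation, and none of the figures allows for the two tests that come first.

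A reader might go further and conclude that a treatment with more deaths could readily be declared better on functional class. The documents do not support that: iNO must first succeed on 6MWD and on TTCW, where deaths count against it.

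**What to change.** 1. In SAP 6.3 and 7.4.2, score death before Week 18 as a category worse than Class IV, and state that every death ranks below every surviving subject's change.
2. Test Week 18 change with a rank-based test stratified by prostanoid use: van Elteren, or CMH row mean scores with rank scores. The plan already uses van Elteren and stratified CMH tests elsewhere.
3. Keep ANCOVA with LOCF as a sensitivity analysis.
4. State in SAP 7.4 that the log-transform step does not apply to WHO class.
5. Align protocol 16.3.2 (primary method), SAP 7.4.2 (ANCOVA) and the SAS code reference in 7.4.2, and record the change in SAP 11, where the table of changes from the protocol is empty.

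The cost is a few lines of SAP text, a matching correction to the protocol and standard code. The small downside is that the main result becomes a rank comparison rather than a mean change in class; the shift table and the sensitivity ANCOVA still describe its size.

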#### **Hypothesis:**

$H_0: \mu_{iNO\ 75} = \mu_{Placebo}$  versus  $H_1: \mu_{iNO\ 75} < \mu_{Placebo}$  for at least one realization.

**SAS code:** Same as primary

**Direction of difference:** Smaller the Better.

**Missing Data:** Please refer to Section 6.3 for missing data imputation. Missing values will be imputed using the LOCF.

No.	Sensitivity Analysis
1	Analysis on Modified Intention to treat Population
2	Analysis on mITT population for all the subjects completing the 18 weeks treatment period

Analysis: Similar to primary for WHO functional class (Table 27).

**Table 27: Summary of WHO Analysis**

Variable	Model	Population/Criteria	Factors
The Change from baseline in WHO functional class	ANCOVA	ITT	Treatment Group, Prostanoid Usage and Baseline Score.
The Change from baseline in WHO functional class	ANCOVA	mITT	Treatment Group, Prostanoid Usage and Baseline Score.
The Change from baseline in WHO functional class	ANCOVA	mITT (All 18 weeks completers)	Treatment Group, Prostanoid Usage and Baseline Score.

Shift table for WHO categories will also be presented.

For open label period change in WHO Functional Class at month 4, 8 and 12 from baseline and week 18 will be analysed using ANCOVA as defined above.

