### 7.6.5 Change in Borg dyspnea Score Immediately Following 6MWT

The change from baseline for Borg Dyspnea at Week 18 will be analyzed using the ANCOVA model with same factors/covariates given for secondary parameter WHO functional class (Table 31).

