#### Hypothesis:

$H_0: \mu_{iNO\ 75} = \mu_{Placebo}$  versus  $H_1: \mu_{iNO\ 75} > \mu_{Placebo}$  for at least one realization.

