**Table 31 Summary of Borg Dyspnea Analysis**

Variable	Model	Population	Factors
The Change from baseline in Borg Dyspnea at Week 18	ANCOVA	ITT	Treatment Group, Prostanoid Usage and Baseline

For open label period change in Borg Dyspnea at month 4, 8 and 12 from baseline and week 18 will be analysed using ANCOVA as defined above.

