## 9.0 Part II Analysis:

The primary objective of part II open label is incidence of AE and SAE. All the tables for Part I AE's will be replicated for Part II to assess long term safety and tolerability.

[figure not shown]
The secondary objective is to evaluate the change from baseline in 6MWD for subjects who change from Placebo to active therapy. Standard descriptive statistics will be presented. No formal statistical analysis is planned.

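### Open-label WHO class and Borg reuse the Part 1 treatment-group ANCOVA when both arms receive iNO, so the treatment term compares early with delayed start and does not estimate the effect of switching

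*SAP*

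**What the plan says.** SAP 7.4.2 defines the Week 18 WHO class analysis as "ANCOVA with treatment group and stratification factor prostanoid usage as factor and baseline WHO functional score as covariates". Under its Hypothesis heading the alternative is one-sided, with iNO lower than placebo, and the direction is given as "Smaller the Better". After Table 27 the same model is extended to Part 2: change at "month 4, 8 and 12 from baseline and week 18 will be analysed using ANCOVA as defined above".

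SAP 7.6.5 analyses Borg at Week 18 with an "ANCOVA model with same factors/covariates given for secondary parameter WHO functional class", and after Table 31 adds: "For open label period change in Borg Dyspnea at month 4, 8 and 12 from baseline and week 18 will be analysed using ANCOVA". The Borg alternative is printed with iNO greater than placebo, although a higher Borg score means more breathlessness (Protocol 11.1.6).

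In Part 2 both original cohorts receive iNO 75 mcg/kg IBW/hr (Table 1 in each document), and the Protocol synopsis states that Part 2 has no placebo.

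6MWD is treated differently. The text at the end of SAP 7.3.1 has open-label 6MWD summarized separately for subjects who moved from placebo to active treatment. SAP 9.0, after naming the 6MWD secondary objective, says: "Standard descriptive statistics will be presented. No formal statistical analysis is planned".

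**The concern.** A treatment-group factor in a period when both groups take the same drug no longer separates drug from placebo. It separates subjects who started iNO at randomization from those who started 18 weeks later, among those who chose to continue. If iNO works and former placebo subjects improve after switching, the arm difference in change from baseline shrinks towards zero. The arm difference in change from Week 18 then favours the former placebo arm. For WHO class, the only alternative the SAP states is in the opposite direction.

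At stake is how the open-label tables are read. A null or reversed arm contrast could appear beside a drug that works in both arms, while the quantity of interest, the switchers' own change, is not named as an output for either measure. The model is also incompletely specified for this use. No open-label hypothesis is given, and the SAP does not say whether the Week 2 or the Week 18 score is the covariate for change from Week 18.

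**Working it through.** The documents give no effect size, SD, sample size or power for open-label WHO class or Borg, so there is no planned figure to reproduce. The check is of direction and rough size.

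**Inputs**
- From the documents: 1:1 allocation; tests one-sided at 0.025 unless otherwise specified (Protocol 16); 75 evaluable subjects per arm (SAP 5.4); 81% uptake of the Phase 2 extension (Protocol 5.1).
- Assumed: iNO benefit at Week 18 of d = 0.3 class; SD of change 0.6, for both change scores; former iNO subjects hold their gain; switchers recover a fraction c of d by the open-label visit. Applying the Phase 2 uptake here is also an assumption: 0.81 × 75 ≈ 61 per arm.

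**Formulas** (iNO minus placebo; negative favours the original iNO arm)
- Change from baseline: −d(1 − c)
- Change from Week 18: +d·c
- SE = 0.6 × √(2/61) = 0.109
- One-sided p for the alternative iNO < placebo, at the expected difference: Φ(difference / SE)

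**Results, WHO class, unadjusted**

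| Catch-up c | From Week 18: difference, z, p | From baseline: difference, z, p |
|---|---|---|
| 0 | 0, 0, 0.5 | −0.30, −2.76, 0.003 |
| 0.5 | +0.15, 1.38, 0.92 | −0.15, −1.38, 0.08 |
| 1 | +0.30, 2.76, 0.997 | 0, 0, 0.5 |

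The contrast from Week 18 runs against the stated alternative for every c above zero. The contrast from baseline fades as switchers catch up.

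**Other assumptions.** With 75 per arm (about 150 in Part 2, Protocol Table 5) and a benefit of 0.3 to 0.5 SD, the WHO alternative for change from Week 18 rejects with probability 0.0001 or less at full catch-up and 0.002 to 0.0002 at half. The opposite direction would reject with probability 0.45 to 0.86 at full catch-up. With no catch-up, either direction rejects 2.5% of the time.

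**Adjusting for the Week 18 score.** With an assumed slope of 0.6, the adjusted difference is −d(1 − c) + 0.6d. For d = 0.3 this is +0.18 at c = 1, +0.03 at c = 0.5 and −0.12 at c = 0. The reversal remains at full catch-up, nearly vanishes at half, and is absent with none.

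**Borg.** A lower score is better, so improving switchers make the iNO-minus-placebo change from Week 18 positive. The printed alternative, iNO greater than placebo, has that same sign. It is the wrong way round for the Part 1 comparison and for change from baseline. If it is corrected to iNO less than placebo, Borg behaves like WHO class in the table.

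**The case against.** The phrase in question names a model. The one-sided hypothesis stands under its own heading for an analysis defined at Week 18, so carrying it into Part 2 is an inference. That is fair, and the wrong-way point is therefore conditional. The Protocol's default of one-sided testing makes the inference reasonable but does not settle it.

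A reader might infer that this model cannot yield the switchers' change at all. The documents do not support that. SAP 7.4.2 refers to the primary SAS code, which requests least-squares means with confidence limits; for change from Week 18, the former placebo arm's mean would estimate the switchers' change. What stands is that no such estimate is named for WHO class or Borg.

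A reader might also infer that these ANCOVAs fail the Part 2 objective, or flatly contradict SAP 9.0. Neither follows. The switcher objective concerns exercise tolerance, its endpoint is 6MWD (Protocol 7.2), and the sentence in SAP 9.0 follows that objective without mentioning WHO class or Borg. Open-label 6MWD is already summarized for switchers separately. The difference in treatment between measures is awkward, but it is not a proven conflict.

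Finally, an early-versus-delayed-start contrast can be interpreted, and both documents make plain that all Part 2 subjects receive iNO. A careful reader would not take a null contrast as no benefit. That limits the consequence but does not make the contrast informative about switching.

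**Conclusion.** The point holds in a limited form. For both measures the open-label treatment term compares early with delayed start among continuers and does not estimate the effect of switching. For WHO class, if the stated alternative is carried over, it is reversed for change from Week 18 whenever switchers improve.

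The size depends on assumptions that the documents do not supply. The one-sided p of about 0.997 is the full catch-up extreme of a range that starts at about 0.5, and it comes from an unadjusted calculation. It should not be read as the expected result. Nor does the wrong-way point extend to Borg as printed; it applies there only once the sign in SAP 7.6.5 is corrected.

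These are supportive analyses. Neither measure is a protocol Part 2 endpoint, neither open-label test is in the SAP 7.5 testing order, and Part 1 conclusions are unaffected. This is a minor improvement that is worth making.

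**What to change.** In SAP 7.4.2 (after Table 27) and 7.6.5 (after Table 31), remove the instruction to use the ANCOVA defined above. In its place, report observed within-subject change from Week 2 and from Week 18 at months 4, 8 and 12, by original arm: mean with 95% CI, plus a shift table for WHO class. Show placebo-to-iNO switchers separately, as SAP 7.3.1 does for 6MWD, and keep the presentation descriptive, as in SAP 9.0. Specify observed data explicitly, because SAP 7.4 and 7.6 apply LOCF generally and do not exempt the open-label visits.

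If a between-arm contrast is kept, label it early versus delayed start, make it two-sided and exploratory, and name the covariate. Correct the Borg sign in SAP 7.6.5 at the same time.

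The cost is SAP wording and somewhat less analysis work. The downside is small: within-subject change has no concurrent control and stays open to time trend and attrition, which the report should say.
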